5.2. Study Days

Following the 7-day pre-study period, which includes time for analysis of the blood and urine, eligible IPF patients will return to the clinic and be admitted to the 21-day study. On the first day of the study, these patients will have a physical exam and their vital signs will be recorded. Then, their degree of nasal inflammation and erythema will be evaluated and recorded as before, as will their SaO2, FEV1 and FVC levels and frequency of coughing. Patients will be instructed on how to self-administer their first dose of the nasal spray drug (0.2% sodium pyruvate in 0.9% sodium chloride solution) by first forcefully expelling air from their lungs, and

then spraying 3 squirts of the drug into each nostril, and then forcefully inhaling the drug so that the drug is inhaled into the lungs. After 1 hour, the subjects will have their vital signs taken again. Efficacy and safety evaluations will occur at this 1-hour time period, too, and then again at 2 and 3 hours. The subjects will fill out the product evaluation questionnaire, be given a daily data log form and be given enough drug to last for 21 days (3 bottles), and released from the clinic.

For the next 21 days, subjects will self-administer 3 squirts per nostril of the nasal spray, as instructed, 3 times daily; upon wakening, noon/midday, and before bedtime, Additionally, they will fill out the Daily Data Log form each day to record the number of daily coughs. Patients will be contacted by phone every 2 days to review symptoms and protocol compliance.

On days 8, 14 and 22, they will return to the clinic and have their blood analyzed, vital signs taken, and their degree of nasal inflammation, erythema and cellular morphology recorded. As before, they will be tested for FEV_1 , FVC and SaO_2 levels. The number of coughs they experienced and other information will be discussed with the clinician. They will fill out the product evaluation questionnaire and the CRDQ, and they will then be released from the study on day 22. These data will then be evaluated.

6. Criteria for Patient Selection, Exclusion of Patients, and Number of Patients 6.1. Subject Selection and Number of Patients to be Studied

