13.2. Safety Testing

- Physical Exam
- Vital Signs
- Weight
- Blood pressure
- Pulse
- Temperature
- Blood analysis
- Complete blood count (CBC)
- Clinical tests, including:
 - Urea nitrogen: serum creatinine: total protein: serum albumin: total globulin: albumin/globulin ratio: total bilirubin: alkaline phosphatase: aspartate aminotransferase (AST or SGOT): alanine aminotransferase (ALT or SGPT): LDH: GGT: serum sodium: potassium: chloride serum: carbon dioxide: total cholesterol:hdl ratio:
- Urine test for women of child-bearing age

- Efficacy tests
 - o Nasal examinations by a rhinoscope fitted with a camera
 - \circ FEV₁, FVC

14. Withdrawal Criteria

The patients can withdraw from the study at any time, and for any reason. All data collected from these patients will be analyzed. Reasons for withdrawal will be recorded to insure that it was not due to an adverse event.

The subject has the right to withdraw from the study at any time.

The subject will be withdrawn from the study if:

- There is deterioration in the subject's signs and symptoms and/or the subject develops a disease or condition that, in the opinion of the investigator, would compromise the subject's safety by continuing in the study.
- In the investigator's judgment, it is in the best interest of the subject.
- There is a violation of the protocol inclusion and/or exclusion criteria, as deemed relevant by the investigator and discussed with the medical monitor.
- The subject begins to take any medication(s) that is(are) excluded by the protocol.
- Any of the conditions for stopping rules are met.

If a subject withdraws prematurely from the study due to the above criteria or any other reason, study staff should make every effort (at withdrawal) to complete the full set of evaluations listed for the early termination/end-of-study visit. The reason for subject withdrawal must be documented in the case report form (CRF).

If a subject withdraws from the study due to an adverse event (AE) (eg, clinical signs, symptoms, or clinically significant laboratory abnormality), the subject will be asked to return to the clinic, at a minimum, for the evaluations scheduled for the posttreatment follow-up period. If the AE has still not resolved, additional follow-up will be performed, as appropriate, and documented in the subject's medical records. As a minimum requirement, AEs should be followed for 30 days after the subject's last dose of study medication.

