In the case of a subject lost to follow-up, attempts to contact the subject must be made and documented in the subject's medical records.

Withdrawn subjects will not be replaced.

15. A Description of Clinical Procedures, Laboratory Tests, or Other Measures to be Taken to Monitor the Effects of the Drug in Human Subjects and to Minimize Risk

Tests and analyses will be conducted 3 times during the study. If any aberrant values occur, the principal investigator will determine if that patient should continue in the study or be removed. All aberrant values that occur during the study will be considered adverse events. A summary of possible risks will be provided to the patients. Previous risks of using the product are minimal, which included irritation to the nose cavity reported by 1 patient out of 1,869.

16. Safety Precautions Included in this Study

The 0.2% nasal sodium pyruvate inhalation has been administered to both healthy humans and humans with lung diseases, without the occurrence of any SAE.

- First administration of nasal spray on the premises of a hospital/clinic.
- The initial nasal spray will be administered under the supervision of medical staff.
- If a subject develops any adverse event during the follow-up period after study drug administration, the subject will be treated to a satisfactory resolution before being discharged from the clinic.
- Subjects will remain at the test site for monitoring for 30 minutes after the initial inhalation of the nasal spray.
- Follow up telephone communications, as needed.

17. Product Evaluation Questionnaire

This self-administered questionnaire measures the patients' impressions of how the drug affected their nasal cavity, their coughing, and their breathing. It is designed to evaluate changes in a subject's quality of life over time. It will be administered during all clinic visits.

18. Daily Data Logbook

Subjects will use this diary card to record the number of their coughs per day, any self-perceived adverse events, and any medication changes during the study.

19. Urinalysis

Samples will be taken and analyzed to determine if any child-bearing females are pregnant.

20. Study Management

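### Section 14 requires adverse events to be followed for 30 days after the last dose, but the last planned contact, Day 22, is at most 21 days after any last dose

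*Combined protocol and SAP*

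**What the plan says.** Section 14 (Withdrawal Criteria) contains several related instructions.

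- Any patient who withdraws early should, at withdrawal, "complete the full set of evaluations listed for the early termination/end-of-study visit".
- For a patient who withdraws because of an AE, "the subject will be asked to return to the clinic, at a minimum, for the evaluations scheduled for the posttreatment follow-up period".
- The same paragraph continues: "If the AE has still not resolved, additional follow-up will be performed, as appropriate". It then closes with the minimum: "As a minimum requirement, AEs should be followed for 30 days after the subject's last dose of study medication".
- For patients lost to follow-up, "attempts to contact the subject must be made and documented".

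The Section 13.1 schedule has columns for Screening and Days 1, 8, 14 and 22 only. The Adverse Events and Blood Sample rows both end at Day 22. Section 5.2 agrees on the visits ("On days 8, 14 and 22, they will return to the clinic and have their blood analyzed") and on the end of participation ("they will then be released from the study on day 22"). Regular calls are planned, but they are described as part of the 21-day dosing period: "Patients will be contacted by phone every 2 days to review symptoms and protocol compliance".

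Other sections also bear on AEs:

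- Section 9 tells patients to ring the clinic about any AE they notice.
- Section 15 counts every aberrant laboratory value during the study as an AE.
- Section 16 allows follow-up calls when needed.
- Section 24 recognises AEs arising after the study, and Section 24.3 requires any AE with onset after enrolment to be recorded.
- Section 24.5 covers serious events after participation ends, if the investigator learns of them and thinks they may be related.

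**The concern.** The protocol sets a 30-day minimum and refers to a scheduled post-treatment period, but its schedule contains neither a 30-day contact nor a period of that name. After Day 22, follow-up begins only if the patient calls, the investigator decides it is appropriate, or a related serious event comes to notice. None of these has a date or a defined content.

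Two groups are exposed. The first is patients who withdraw because of an AE that has not resolved by their last scheduled visit. The second is completers whose AE is open or first found at Day 22. For the second group it is also unclear whether the 30-day rule applies, because the sentence sits in the paragraph on withdrawal for an AE.

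Day 22 bloods are the clearest case. An abnormal result is an AE under Section 15. Section 5.2 allows for laboratory analysis time within the pre-study week, so results are not assumed to be immediate. A Day 22 result may therefore arrive after the patient has been released, and no later draw or call is planned.

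What is at stake is even, complete recording of AE outcomes. The efficacy comparison is not involved.

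**Working it through.** The 30 days is a stated requirement, so there is no derived figure to reproduce. The check is whether any scheduled contact can meet it.

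**Inputs**

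- Required follow-up: 30 days after the last dose (Section 14).
- First dose: Day 1, in the clinic (Section 5.2).
- Last dose for a completer: Day 21 if Day 1 counts as the first of the 21 dosing days, or Day 22 if the 21 days follow Day 1. The drug-administration row of Section 13.1 is marked at Day 22, so a Day 22 dose is possible.
- Last scheduled contact: Day 22 (Sections 5.2 and 13.1).

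**Formulas**, for a last dose on Day d, with d from 1 to 22:

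- days from last dose to Day 22 = 22 − d
- study day of the 30-day point = d + 30
- days by which the 30-day point falls after Day 22 = (d + 30) − 22 = d + 8

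| Last dose (Day d) | Days to Day 22 (22 − d) | 30-day point (d + 30) | Days after Day 22 (d + 8) |
|---|---|---|---|
| 1 | 21 | Day 31 | 9 |
| 8 | 14 | Day 38 | 16 |
| 14 | 8 | Day 44 | 22 |
| 21 | 1 | Day 51 | 29 |
| 22 | 0 | Day 52 | 30 |

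The largest gap between last dose and Day 22 is 21 days, for a patient dosed only on Day 1. That is still 9 days short of 30. No last-dose day lets Day 22 meet the minimum.

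**Do the other provisions supply a planned contact at 30 days?**

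- Section 9: initiated by the patient.
- Section 14, further follow-up of unresolved AEs: at discretion in form and timing, above the 30-day floor.
- Section 14, contact attempts: only for patients lost to follow-up.
- Section 16: calls as required, no date.
- Sections 24 and 24.3: recording rules, no contact.
- Section 24.5: serious, possibly related events that reach the investigator. A non-serious event such as nasal irritation falls outside it.

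None does.

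**Cost of adding one**

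One call every 2 days for 21 days is 21 / 2, or about 10 calls per patient. For 50 patients that is about 500 planned calls. One more per patient is 50, and 50 / 500 = 10%.

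**The case against.** The strongest case on the other side has four parts.

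First, scope. The 30-day sentence closes a paragraph about patients who withdraw because of an AE, and it concerns AEs that exist. A patient without an AE has nothing to follow. This stands. A reader might infer that the protocol breaks its own rule for all 50 planned patients, or that each missing outcome costs 4% of an arm (1/25). The documents do not support either reading. The rule may not apply to most patients, and a patient whose AE outcome is unknown still counts in AE incidence.

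Second, the remaining visits. A patient who stops on Day 10 because of an AE still has Days 14 and 22 ahead, with examination, bloods, vital signs and AE review. These can reasonably be read as post-treatment evaluations. This stands in part: they serve early withdrawals, but only up to Day 22.

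Third, the duty exists. Thirty days is called a minimum, so the discretionary wording on further follow-up does not remove it, and nothing forbids contact after Day 22. This also stands. A reader might infer that AEs are abandoned at Day 22, and the text does not say so. What it lacks is a planned means of reaching the 30-day point.

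Fourth, low risk. Section 15 cites nasal irritation in 1 of 1,869 prior patients, which scales to 50 / 1,869, or about 0.03 patients here. Sections 1.1.3.5 and 1.1.3.6 give a 15-minute half-life for injected pyruvate. These points limit the weight of the concern. However, the 1 in 1,869 describes reported product risk and does not cover all-cause AEs or abnormal laboratory values. A reader might infer that delayed toxicity is being missed; nothing in the documents suggests it, and it is not claimed here.

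It can also be said that asking every patient about new AEs goes beyond following known ones. That is true. It is offered as an inexpensive improvement and is not something Section 14 already demands.

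**Conclusion.** The point holds in a limited form. The protocol sets a 30-day minimum for following AEs, but its last planned contact is 0 or 1 day after a completer's last dose and at most 21 days after anyone's. The 30-day point lies 9 to 30 days beyond that contact. The duty to follow existing AEs remains, and event-driven follow-up is allowed. AEs open or found at Day 22 in completers, including abnormal Day 22 bloods, have no scheduled follow-up.

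The number of patients affected cannot be derived, because the documents give no expected AE or withdrawal rate. Efficacy results and error rates are unaffected. This is a change that should be made, mainly because it is cheap; it does not threaten the trial's validity.

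The conclusion assumes that the calls every 2 days stop with dosing, as their placement in Section 5.2 implies. It also assumes that a completer's last dose is on Day 21 or 22.

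**What to change.** Make three changes.

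1. Add to Section 13.1 one telephone safety contact 30 days after the last dose for each dosed patient. For completers this is Day 51 or 52; for others it is the last-dose day plus 30. Record the outcome of every open AE and any new AE or serious AE.
2. Require a repeat test for any clinically significant abnormal Day 22 blood value.
3. State in Section 14 that the 30-day minimum applies to any AE open at withdrawal or at Day 22.

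Section 20.3 requires specific consent for follow-up after withdrawal from the intervention if the original form did not describe it. The consent form should therefore mention the call.

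The cost is about 50 calls, or about 10% more than the roughly 500 planned, plus a few repeat tests whose number cannot be derived. Safety close-out moves to about 30 days after the last patient's Day 22. The documents describe no separate data lock, so the plan should say that efficacy data are locked after the last Day 22 visit. The efficacy analysis is then not delayed.

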20.1. Case Report Forms

Case Report Forms (CRF) will be supplied by Cellular Sciences. Data will be recorded in the CRFs according to the following:

Instructions to data entry personnel and monitor:

Explain all missing data and include reference to any original data that is not contained in the study file. If a space is blank because the item was not done, mark the item "N/D". If the item is not applicable to the individual case, mark the item "N/A". If an item is unknown, mark the space "UNK". Legibly write or print all entries in black ink. If an entry error has been made, draw a single straight line through the wrong entry and enter the correct data above it. Initial and date all such changes. Do not erase or opaque out errors. For clarification of illegible or uncertain entries, print the clarification above the item, then initial and date the clarification.

20.2. Data Collection, Management, and Statistical Analysis

The data management staff at the research clinic will collect and manage the data. Data will be obtained, maintained, and transmitted securely in accordance with HIPAA guidelines. Monitoring and auditing of the data will be conducted by a staff member of Cellular Sciences.

Statistical analysis will be performed on deidentified data. The basic statistical analysis will be repeated measurements of Analysis of Variance using baseline measurements as a covariant (ANCOVA). Age, sex, time since initial diagnosis with IPF, concurrent medications and smoking status are considered potential covariates. Number of coughing episodes reported for a 24-hour pre-study period, and other pre-study data information, will be compared to the data collected during the trial. The differences between baseline data and the data collected during the trial will be compared and analyzed (Within treatment). Additionally, the data of the patients on the experimental therapy will be compared to the data generated by the patients on placebo (Between treatments). P values of <0.5 will be considered significant. FEV1 and FVC will similarly be analyzed as secondary outcome measurements. Relative changes will be analyzed by JMP, Matillion, XLSTAT or R software by [name] or [name], who will be responsible for the statistical analysis.

Partial patient data will be included in the statistical analysis if patients withdraw from the study, but data from non-compliant patients will be excluded. Our previous research (REF) indicates that a sample size of 20 is sufficient to detect a statistically significant difference (p<0.05) between treatment groups. We have chosen to enroll 25 patients in each treatment group to ensure we achieve the necessary sample size, taking into account that some patients may not complete the study, and some data will be incomplete or excluded from the study.

Study Monitoring Sciences. The monitor will visit the clinical frequently during the trial to assure that all data are being collected and that the Case Report Forms are completed and correctly filled out. The CRFs and related source documents will be reviewed in detail by the study monitor at each visit, in accordance with relevant SOPs and ICH GCP regulations. This includes results of tests performed as a requirement for participation in this study and any other medical records required to confirm information contained in the CRFs, such as past medical history and secondary diagnoses. The investigator and staff will be expected to cooperate with the study monitor and provide any missing or incomplete information whenever possible.

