1.1.6. Prior Sodium Pyruvate Treatment in Pulmonary Fibrosis and IPF Studies

A phase 2 study was designed to demonstrate safety, efficacy, and determine which medical endpoints produced clinically and statistically significant results. Inflammatory pathways are upregulated in the nasal epithelium in 80% of patients with IPF, which is part of the etiology of

the disease that effects all lung functions (28). Inflammation induced oxidative stress decreases lung functions including FEV_1 and FVC values and increases mucus and coughing. Nasal steroids and OTC products have been ineffective in treating these conditions in IPF patients, especially when these patients experience exacerbation do to stress or allergies.

Coughing frequency is high in patients with advanced IPF, with median (range) 24-h cough counts varying from 226 (36–946) to 520 (117–1493) depending on the population studied (34-41). In mild to moderate cases in IPF patients, cough counts vary from 4-57 per 24-h. Strikingly, IPF patients experience more cough symptoms during the daytime (median hourly cough rate 14.6 during the day versus 1.9 during the night) (34-41). Chronic cough in IPF is not related to age or gender and is more common in advanced disease and in "never-smokers" (34-41). There is no clear explanation why IPF patients without a history of smoking cough more.

An initial 21-day sub-chronic clinical trial was conducted that included 15 patients with pulmonary fibrosis (9 with pulmonary fibrosis and chronic obstructive pulmonary disease (COPD) and 6 with idiopathic pulmonary fibrosis without COPD) that remained on their normal medications, but were also administered the 20 mM (2.2 mg/mL) sodium pyruvate nasal spray. If the patients were using other nasal sprays as part of their normal therapy, the other nasal spray was eliminated. In all 15 patients, the test results were compared to their previous 3-week screening and baseline data (their current therapies) as the positive control for each variable including all their lung functions, FEV₁, FVC, PEF, FEV₁/FVC ratios, SaO₂, nitric oxide, coughing rates and nasal inflammation (23).

Results

Coughing

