2.1. Primary Objective

Reduce coughing episodes in IPF patients by 25%. (An episode is defined as 5 or more coughs per hour.)

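### Section 20.2 does not state the scale of the cough analysis, although the target is a percentage and counts vary widely; untransformed counts would miss the 25% question and lose some power

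*Combined protocol and SAP*

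**What the plan says.** Section 20.2 gives the method in one sentence: "The basic statistical analysis will be repeated measurements of Analysis of Variance using baseline measurements as a covariant (ANCOVA"). It lists possible further covariates and calls for within-treatment and between-treatment comparisons. It then says that relative changes will be analysed in one of several software packages. It gives no outcome scale, transformation, count distribution or effect measure, and does not say whether a relative change is a percent change, a ratio or a log ratio.

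The primary objective in Section 2.1 is to "Reduce coughing episodes in IPF patients by 25" per cent, and adds: "An episode is defined as 5 or more coughs per hour". The diary (Section 18) records coughs per day.

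Section 1.1.6 gives median 24-hour counts in advanced IPF of 226 (range 36–946) and 520 (117–1493), "depending on the population studied (34-41). In mild to moderate cases in IPF patients, cough counts vary from 4-57 per 24-h". Section 6.1 enrols mild to moderate patients.

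On size, Section 20.2 says that "a sample size of 20 is sufficient to detect a statistically significant difference (p<0.05) between treatment groups" and that "We have chosen to enroll 25 patients in each treatment group to ensure we achieve the necessary sample size".

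**The concern.** The objective is relative, but the named model is additive unless a scale is given. If a drug removes a quarter of all coughs, a patient at 4 per day loses 1 (4 × 0.25) and a patient at 57 loses about 14 (57 × 0.25 = 14.25). One absolute difference describes neither patient, its size depends on the case mix, and it cannot be set directly against 25%. The variance will also tend to rise with the count, so a few heavy coughers dominate the estimate.

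Two things are at stake in a 50-patient trial. One is power. The other is whether the result answers the stated question. Leaving the scale open also lets it be chosen after the data are seen.

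**Working it through.** **The plan's own figure.** The stated 20 cannot be reproduced, because power, SD, sidedness and baseline correlation are not given. It can be back-solved at two-sided 0.05 and 80% power, reading 20 as per arm:

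- Standardized effect needed: (1.960 + 0.842) × √(2/20) = 0.886.
- A 25% reduction on the log scale: ln 0.75 = −0.288.
- Largest residual log SD that 20 per arm can tolerate: 0.288/0.886 = 0.325. At 25 per arm it is 0.363.

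**Spread implied by the documents.** The ranges give a log SD only under an assumption about how many SDs they cover.

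- Mild to moderate, 4–57: ln(57/4) = 2.66. Log SD is 0.66 if the range spans 4 SD and 0.44 if it spans 6 SD.
- Advanced, 36–946: ln(946/36)/4 = 0.82.
- Advanced, 117–1493: ln(1493/117)/4 = 0.64.

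The skew is visible in the advanced-disease figures: 520 lies 403 above its minimum and 973 below its maximum. No median is given for mild to moderate disease.

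**Simulation.** Baseline and follow-up were lognormal with a true ratio of 0.75. There was one follow-up summary per patient, weekly-mean Poisson noise in the low-count cases (median 15 assumed), 20,000 trials per cell and two-sided 0.05. Each analysis was an ANCOVA with baseline as covariate. The correlation ρ between log baseline and log follow-up is assumed. Gaps are differences of the powers shown.

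| Log SD | n/arm | ρ | Raw | % change | Log | Log − raw | Log − % change |
|---|---|---|---|---|---|---|---|
| 0.50 | 25 | 0.5 | 53.3% | 49.6% | 58.9% | 5.6 | 9.3 |
| 0.50 | 25 | 0.95 | 99.3% | 99.2% | 99.5% | 0.2 | 0.3 |
| 0.66 | 20 | 0.8 | 44.9% | 48.7% | 54.4% | 9.5 | 5.7 |
| 0.66 | 25 | 0.5 | 32.7% | 29.4% | 39.7% | 7.0 | 10.3 |
| 0.66 | 25 | 0.8 | 54.3% | 59.0% | 65.1% | 10.8 | 6.1 |
| 0.82 | 20 | 0.8 | 30.3% | 38.4% | 43.3% | 13.0 | 4.9 |
| 0.82 | 25 | 0.9 | 57.4% | 75.7% | 78.6% | 21.2 | 2.9 |

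Over the full grid (ρ 0.5–0.95, 20 and 25 per arm), log beat raw by about 0 to 11 points at the 4–57 spread. Runs with median 20 and separate between-patient and within-patient variation gave 7 to 13 points at total log SD 0.53–0.66. Together these give 0 to 13. At log SD 0.82 the gap was 6 to 21 points.

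**Type I error.** With no effect, rejection rates were 3.9–5.1% on raw counts and 4.8–5.2% on logs.

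**Episodes.** Assume Poisson coughs, a 16 h day and an 8 h night, and use the 14.6 to 1.9 day-to-night hourly ratio of Section 1.1.6. For 15 coughs per day the daytime rate is 15/(16 + 8 × 1.9/14.6) = 0.88 per hour. An hour with 5 or more coughs is then so rare that about 97% of days have no episode. A day with 4 coughs cannot contain one. A plain log is undefined for such data.

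**The case against.** The strongest reply is that the plan never commits to raw counts. The scale is simply unstated, and the sentence on relative changes leaves percent change open, which would be on the right footing for a 25% target. This stands, so the fault is an unspecified scale, not a declared raw-count analysis. It does not remove the point: percent change still gives up about 0 to 10 points to the log scale, and the plan does not choose between them.

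A second reply is that this is a matter of efficiency. It stands too. Type I error is sound, and the sample size is the larger problem. At log SD 0.66 and ρ 0.8 the residual SD is 0.66 × √(1 − 0.64) = 0.396. Twenty per arm then gives about 63% power even on the log scale by normal approximation, and 54% in the simulation with Poisson noise. The sentence "P values of <0.5 will be considered significant" is a separate error, and the calculations here use 0.05 throughout.

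A reader might go further and infer that the plan analyses raw counts and so forfeits 10 to 19 points. The documents do not support that. The top of that range needs a between-patient log SD of 0.80 with within-patient SD 0.3–0.4 added, a total of √(0.64 + 0.09) = 0.85 to √(0.64 + 0.16) = 0.89. The 4–57 range would then span only about 3 SD (2.66/0.85 = 3.1). The clearest evidence of skew is also from advanced disease, which this trial does not enrol.

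**Conclusion.** The point holds as a cheap improvement that the sponsor should make. Section 20.2 names a normal-theory model for coughing without a scale, against a relative target and widely spread counts. Untransformed counts would leave the 25% question unanswered. Under a multiplicative effect with 20 to 25 per arm, they would cost roughly 0 to 13 points of power at the 4–57 spread, and up to about 20 only at the spread of advanced disease. Percent change would cost about 0 to 10.

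The direction was the same in every scenario run. The size depends on assumed SDs, correlations and medians, and on daily cough counts as the outcome; it does not carry over to episodes. The simulation also reduces the repeated measures to one summary per patient. Nothing here shows an inflated false-positive rate. Confidence is medium.

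**What to change.** First reconcile the endpoint. Section 2.1 is written in episodes, while the diary collects coughs per day, so hourly episodes cannot be derived from it.

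Then state in Section 20.2:

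- **Outcome:** each patient's mean daily cough count from the diary, over a named treatment window. Section 5.2 has the log kept daily for 21 days, but the footnote to Section 13.1 stops it at day 14, so the window must be settled.
- **Model:** log outcome, with a small prespecified constant for zeros and log baseline as covariate; or a negative binomial model with log link and log baseline.
- **Baseline:** the 7-day pre-study diary of Section 5.1, in place of the 24-hour pre-study period now in Section 20.2.
- **Report:** the N115/placebo ratio with 95% CI, set against 0.75.

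If episodes are kept, they must be collected hourly and analysed with a count model that handles zeros, not a log transform.

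If daily counts are adopted, the cost is a few sentences. R, already listed, can fit these models, and no extra patients or visits are needed. The downside is that results are ratios of geometric means or of rates, which some readers find less direct than a difference in coughs per day.
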